10.2.4 Suspected Unexpected Serious Adverse Events

Suspected unexpected serious adverse reactions (SUSARs) are serious events that are not listed in the Development Core Safety Information (DCSI) in the IB and that the treating physician identifies as related to the IP or study procedure. United States 21 Code of Federal Regulations (CFR) 312.32 and European Union Clinical Trial Directive (CTD) 2001/20/EC and the associated detailed guidances or national regulatory requirements in participating countries require the reporting of SUSARs. Lilly has procedures that will be followed for the recording and expedited reporting of SUSARs that are consistent with global regulations and associated detailed guidances.

10.2.5 Adverse Events of Special Interest (AESIs)

Adverse events of special interest, which may or may not be associated with ramucirumab therapy, include infusion-related reactions, hypertension, arterial or venous thrombotic events, bleeding (hemorrhagic) events, proteinuria, gastrointestinal perforation, reversible posterior leukoencephalopathy syndrome (RPLS), congestive heart failure (CHF), impaired wound healing, and liver failure and other significant liver injury. The worst grade of each of these events, if they occurred, will be reported on the designated CRF at the time the patient discontinues ramucirumab therapy.

10.2.6 Infusion-related Reactions

Infusion-related reactions are defined according to the NCI-CTCAE Version 4.03 definition of [Type here] [Type here] [Type here]

allergic reaction/hypersensitivity, as follows:

- Grade 1: Mild, transient reaction; infusion interruption not indicated; intervention not indicated
- Grade 2: Therapy or infusion interruption indicated but responds promptly to symptomatic treatment (for example, antihistamines, NSAIDs, narcotics, I.V. fluids); prophylactic medications indicated for ≤ 24 hours
- Grade 3: Prolonged (for example, not rapidly responsive to symptomatic medication and/or brief interruption of infusion); recurrence of symptoms following initial improvement; hospitalization indicated for clinical sequelae
- Grade 4: Life-threatening consequences; urgent intervention indicated

Consistent with usual medical practice, selected parenteral medications may be utilized for Grade 2 allergic/hypersensitivity reaction as detailed below.

The following are suggested treatment guidelines for all infusion-related reactions:

Grade 1 Slow the infusion rate by 50%.

- Monitor the patient for worsening of condition.
- For subsequent infusions, premedicate with diphenhydramine hydrochloride 50 mg I.V. (or equivalent); additional premedication may be administered at the discretion of the patient's physician.

Grade 2

- Stop the infusion.
- Administer diphenhydramine hydrochloride 50 mg I.V. (or equivalent), acetaminophen 650 mg orally for fever, and oxygen.
- Resume the infusion at 50% of the prior rate once the infusion reaction has resolved or decreased to Grade 1; the infusion duration should not exceed 2 hours.
- Monitor for worsening of condition.
- For subsequent infusions, premedicate with diphenhydramine hydrochloride 50 mg I.V. (or equivalent); additional premedication may be administered at the discretion of the patient's physician.

For a second Grade 1 or 2 infusion reaction, administer dexamethasone 8-10 mg I.V. (or equivalent); then, for subsequent infusions, premedicate with diphenhydramine hydrochloride 50 mg I.V. (or equivalent), acetaminophen 650 mg orally, and dexamethasone 8-10 mg I.V. (or equivalent).

Grade 3

[Type here]

[Type here]

[Type here]

Pembrolizumab + Ramucirumab (Ver 2.5, Oct 2024)

- Stop the infusion and disconnect the infusion tubing from the patient.
- Administer diphenhydramine hydrochloride 50 mg I.V. (or equivalent), dexamethasone 8-10 mg I.V. (or equivalent), bronchodilators for bronchospasm, and other medications/treatment as medically indicated.
- Patients who have a Grade 3 infusion reaction must not receive further treatment with ramucirumab.

Grade 4

- Stop the infusion and disconnect the infusion tubing from the patient.
- Administer diphenhydramine hydrochloride 50 mg I.V. (or equivalent), dexamethasone 8-10 mg I.V. (or equivalent), and other medications/treatment as medically indicated.
- Give epinephrine or bronchodilators as indicated.
- Hospital admission for observation may be indicated.
- Patients who have a Grade 4 infusion reaction must not receive further treatment with ramucirumab and will be cared for at the discretion of the treating physician.

The specific infusion related reaction to pembrolizumab will be managed as follows;

NCI CTCAE Grade	Treatment	Premedication at subsequent dosing
Grade 1 Mild reaction; infusion interruption not indicated; intervention not indicated	Increase monitoring of vital signs as medically indicated until the subject is deemed medically stable in the opinion of the investigator.	None
Grade 2 Requires infusion interruption but responds promptly to symptomatic treatment (e.g., antihistamines, NSAIDS, narcotics, IV fluids); prophylactic medications indicated for <=24 hrs	Stop Infusion and monitor symptoms. Additional appropriate medical therapy may include but is not limited to: IV fluids Antihistamines NSAIDS Acetaminophen Narcotics Increase monitoring of vital signs as medically indicated until the subject is deemed medically stable in the opinion of the investigator. If symptoms resolve within one hour of stopping drug infusion, the infusion may be restarted at 50% of the original infusion rate (e.g., from 100 mL/hr to 50 mL/hr). Otherwise dosing will be held until symptoms resolve and the subject should be premedicated for the next scheduled dose. Subjects who develop Grade 2 toxicity despite adequate premedication should be permanently discontinued from further trial treatment administration.	Subject may be premedicated 1.5h (± 30 minutes) prior to infusion of pembrolizumab (MK-3475) with: Diphenhydramine 50 mg po (or equivalent dose of antihistamine). Acetaminophen 500-1000 mg po (or equivalent dose of antipyretic).
Grades 3 or 4 Grade 3: Prolonged (i.e., not rapidly responsive to symptomatic medication and/or	Stop Infusion. Additional appropriate medical therapy may include but is not limited to: IV fluids Antihistamines NSAIDS	No subsequent dosing

[Type here]

[Type here]

[Type here]

Pembrolizumab + Ramucirumab (Ver 2.5, Oct 2024)

NCI CTCAE Grade	Treatment	Premedication at subsequent dosing
brief interruption of infusion); recurrence of symptoms following initial improvement; hospitalization indicated for other clinical sequelae (e.g., renal impairment, pulmonary infiltrates) Grade 4: Life-threatening; pressor or ventilatory support indicated	Acetaminophen Narcotics Oxygen Pressors Corticosteroids Epinephrine Increase monitoring of vital signs as medically indicated until the subject is deemed medically stable in the opinion of the investigator. Hospitalization may be indicated. Subject is permanently discontinued from further trial treatment administration.	
Appropriate resuscitation equipment should be available in the room and a physician readily available during the period of drug administration.		

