8.2 Materials and Supplies

For instructions on reconstitution and administration of ramucirumab, refer to the IB (Safe Handling and Administration). Calculate the dose and volume of ramucirumab needed to prepare the infusion solution. Vials contain either 100 mg or 500 mg as a 10 mg/mL solution of ramucirumab. Only use sterile sodium chloride (0.9%) solution for injection as a diluent.

Administer via an infusion pump. A separate infusion line must be used for the infusion and the line must be flushed with sterile sodium chloride (0.9%) solution for injection at the end of the infusion.

As infusion-related reactions (IRRs) may occur during or after the administration of ramucirumab, premedication is recommended with a histamine H1 antagonist (such as, diphenhydramine hydrochloride or equivalent) intravenously prior to administration of ramucirumab.

If a patient experiences a Grade 1 or 2 IRR, premedication must be given for all subsequent infusions. If a patient has a second Grade 1 or 2 IRR, administer dexamethasone (or equivalent); then, for subsequent infusions, premedicate with diphenhydramine hydrochloride (or equivalent)

Vials should be stored in a refrigerator at 2°C to 8°C (36°F to 46°F) until time of use. Keep the vial in the outer carton in order to protect from light. DO NOT FREEZE OR SHAKE the vial.

The chemical and physical stability for the ramucirumab infusion solution was demonstrated for up to 24 hours at 2°C to 8°C (36°F to 46°F) or for 4 hours at room temperature (below 25°C (77°F)). DO NOT FREEZE OR SHAKE the ramucirumab infusion solution.

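### The infusion-reaction list in 10.2.6 headed for all reactions conflicts, as worded, with the pembrolizumab table on a repeat Grade 2 reaction, and the scope of the stop and same-day attribution are left open

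*Combined protocol and SAP*

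**What the plan says.** Section 10.2.6 opens its management advice with "The following are suggested treatment guidelines for all infusion-related reactions". No drug is named in that heading. For a first Grade 1 or Grade 2 reaction the list says "For subsequent infusions, premedicate with diphenhydramine hydrochloride 50 mg I.V. (or equivalent". For a repeat it says "For a second Grade 1 or 2 infusion reaction, administer dexamethasone 8-10 mg I.V. (or equivalent); then, for subsequent infusions, premedicate with diphenhydramine hydrochloride", together with further agents. Its Grade 3 bullet reads "Patients who have a Grade 3 infusion reaction must not receive further treatment with ramucirumab", and the Grade 4 bullet also names ramucirumab only.

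Section 8.2, within the ramucirumab preparation and handling text, gives the same second-reaction sequence: "If a patient has a second Grade 1 or 2 IRR, administer dexamethasone (or equivalent". Appendix 2, the ramucirumab safety language, repeats the Grade 3–4 stop for ramucirumab.

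Section 10.2.6 then starts a table with "The specific infusion related reaction to pembrolizumab will be managed as follows". Its Grade 1 row gives no premedication at later doses. Its Grade 2 row ends with "Subjects who develop Grade 2 toxicity despite adequate premedication should be permanently discontinued from further trial treatment administration". Its Grade 3–4 row also ends trial treatment permanently.

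The pembrolizumab dose-modification table in 8.4.1 has an infusion-reaction row for Grade 3–4 only.

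On what happens to the partner drug, the Synopsis continues pembrolizumab if ramucirumab is stopped for intolerable toxicity, while section 7.1 discontinues pembrolizumab when ramucirumab stops.

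**The concern.** The first list already premedicates after a first reaction, so a second Grade 2 reaction will normally be one that occurred despite premedication. That is the event for which the pembrolizumab table requires a permanent stop. With the first heading worded to cover every infusion reaction, one pembrolizumab event meets two instructions within one section: further infusions with wider premedication, or permanent discontinuation.

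What is at stake is consistent and safe handling of these patients, and a reliable count of who stopped which drug and why. In a single-arm trial of two antibodies, exposure and discontinuation are part of what gets reported, and they should not depend on which half of a section the treating physician read.

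**Working it through.** The point rests on no sample size, power or event count, so the check is a comparison of the texts plus one schedule count.

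**1. The three sources side by side**

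| Event | 10.2.6, first list | 10.2.6, pembrolizumab table | 8.4.1, pembrolizumab table |
|---|---|---|---|
| First Grade 1 | Premedicate later infusions | No premedication | No entry |
| Second Grade 2, after premedication | Treat, then continue with wider premedication | Permanent stop of trial treatment | No entry |
| Grade 3–4 | No further ramucirumab | Permanent stop of trial treatment | Permanent stop |

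**2. Which drug the first list is for.** The heading says all reactions. Three things point to ramucirumab: the Grade 3 and 4 bullets name only that drug, section 8.2 repeats the second-reaction sequence in ramucirumab text, and Appendix 2 carries the matching Grade 3–4 stop. The list is also described as suggested, whereas the pembrolizumab table is introduced as how reactions will be managed. If the heading is limited to ramucirumab, the first two rows of the table become two drug-specific lists and no longer conflict. As worded, they conflict for pembrolizumab.

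**3. Whether 8.4.1 adds a contrary rule.** Its infusion-reaction row starts at Grade 3. Footnote 2, on persistent or intolerable Grade 2 events, is attached to the row for all other drug-related toxicity, and the general note concerns recurrent Grade 3 or life-threatening events. Nothing there says that dosing continues after a repeat Grade 2 infusion reaction. The two pembrolizumab tables therefore differ by omission.

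**4. What trial treatment covers.** Elsewhere section 10.2.6 names the drug when it means one drug. The pembrolizumab stopping rule names none and does not say both. The rest of the protocol does not settle it: the Synopsis and 7.1 disagree on pembrolizumab after ramucirumab stops, and I found no passage on ramucirumab after pembrolizumab stops.

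**5. How often attribution can be in doubt.** The Synopsis gives ramucirumab every 14 days (D1, D15, D29) and pembrolizumab every 21 days (D1, D22) in a 42-day cycle. The only common day is D1, so the shares given on a shared day are:

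- ramucirumab: 1/3 of doses
- pembrolizumab: 1/2 of doses

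On those days pembrolizumab is infused first and ramucirumab follows. Section 8.2 accepts that ramucirumab reactions may occur during or after administration. No passage says which list applies when the responsible drug is unclear. These shares show how often the question can arise. They are not a rate of reactions or of conflicting instructions.

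**The case against.** The strongest reply is that the section can be read in order without difficulty. A general, suggested list with ramucirumab stopping rules is followed by a specific, mandatory table for pembrolizumab, and the specific text displaces the general. Much of this stands. For a reaction clearly due to ramucirumab there is no conflict. For one clearly due to pembrolizumab, most physicians would go to the pembrolizumab table. The fixed infusion order also helps attribution.

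The reply does not dispose of the point. The protocol states no order of precedence and the heading says the opposite of the intended limit. The specific-over-general reading needs a known causal drug, which D1 may not supply. It also leaves 8.4.1 and the meaning of trial treatment as they are.

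Several stronger readings are tempting and are not supported:

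- A reader might count three opposite outcomes, with 8.4.1 as the third. That table is silent on Grade 2; silence is not an instruction to continue.
- A reader might conclude that a repeat Grade 2 pembrolizumab reaction ends both drugs, in contrast to a Grade 3–4 ramucirumab reaction that ends one. The first half is an inference from an undefined phrase. The second half holds under the Synopsis but not under 7.1.
- A reader might see a contradiction in the Grade 2 row because premedication is put as an obligation in one column and an option in the other. The obligation follows a condition, namely symptoms that did not resolve within an hour of stopping the infusion, so the two can stand together.
- A reader might translate the ambiguity into percentage points of ORR. The documents give no reaction rate. Section 10.1.1 keeps assessing patients who stop treatment before progression, and 13.1.1 keeps every dosed patient in the ORR denominator.

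**Conclusion.** The point holds as a wording defect with safety relevance. Four things need correcting: a heading whose literal scope conflicts with the pembrolizumab table; a Grade 2 stopping rule present in one pembrolizumab table and absent from the other; a stopping phrase that does not say which drug or drugs it covers; and no governing list for a reaction of uncertain cause on D1.

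Its size is limited. It changes neither the two-stage design nor the ORR definition, and no effect on the response rate can be calculated from the documents. Exposure and discontinuation counts could differ with the reading adopted. The conclusion assumes that the first list is meant for ramucirumab, which the surrounding text supports but does not state. No view is taken on which clinical rule is right.

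**What to change.** Reconcile 8.2, the pembrolizumab table in 8.4.1 and both parts of 10.2.6, reading them with the Synopsis and 7.1:

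1. Limit the heading of the first list in 10.2.6 to the drug it is meant for.
2. Make the pembrolizumab tables in 8.4.1 and 10.2.6 agree on a repeat Grade 2 reaction.
3. State which drug or drugs trial treatment covers in the stopping rules, and resolve the disagreement between the Synopsis and 7.1 on continuing pembrolizumab once ramucirumab stops.
4. State which list governs a reaction on a shared dosing day when the causal drug is uncertain.

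The content of each rule is for the investigators to decide. The cost is protocol wording only, with no change to the sample size or the analysis.

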10.3 Biomarker Evaluation

We will conduct Biomarker Research on specimens collected during this clinical trial. This research may include genetic analyses(DNA), gene expression profiling (RNA), proteomics, metabolomics (serum, plasma) and/or the measurement of other analytes.

Genomic analysis: Whole Exome Sequencing at baseline if it is feasible, RNA-seq pre and post (Whole Exome Sequencing/RNA sequencing will be performed at SMC using vendor (Macrogen INC., Korea) and analyzed together with the BI team at SMC with Merck MSD or Lilly.

The objective of collecting specimens for Biomarker Research is to explore and identify biomarkers that inform the scientific understanding of diseases and/or their therapeutic treatments. Integrative genomic analysis (i.e. gene signature, etc.) measured may be a predictive biomarker for patients who receive pembrolizumab treatment.

Integrative immune-genomic analysis to identify association of response with prevalent markers (e.g. PD-L1 expression, EMT signature, T-cell and cytolytic immune signatures, RNA-seq, hypermutation, cfDNA cancer panel genomics).

Pre and post (on-drug biopsy at 6 weeks): RNA sequencing and cfDNA cancer panel genomics to understand the mechanism of action of pembrolizumab/ramucirumab in responders and non-responders.

Pre and post (at baseline, at 3-week and at 6-week post-treatment) to evaluating immune-priming effect of chemotherapy alone and pembrolizumab:

- i) The assessment of plasma or cell free tumor DNA (ctDNA) variant allele frequency (VAF) and tumor mutation burden (TMB) at baseline, at 3-week and at 6-week post-treatment;
- ii) The assessment of integrated molecular profiling (including T cells-

[Type here]

[Type here]

[Type here]

Pembrolizumab + Ramucirumab(Ver 2.5, Oct 2024)

CD3+,CD8+,CD45RO+, Tregs-FOXP3+ and macrophages-CD163+, MHC-1, and PDL1 expression) will be assessed using single cell sequencing (blood and tissue) via 10X genomics.

As an exploratory analysis, we will isolate T cells using FACS sorting and sequence these cells. In addition, in order to identify the relationship between neoantigen drivers like infection and response to pembrolizumab, we will prospectively collect serum antigens from blood at baseline. FACS (Cytex) 20-panel antibody will be used.

11. Adverse Events and Dose Modification

11.1 Ramucirumab

11.1.1 Hypertension

If a patient develops hypertension while on protocol therapy, he or she should be treated with antihypertensive medications according to standard medical practice.

Grade <3

- For controlled hypertension (<160/100 mm Hg), ramucirumab therapy should continue without interruption.
- For asymptomatic hypertension, continue ramucirumab with initiation of antihypertensive therapy.
- If the hypertension is associated with symptoms, hold ramucirumab until symptoms resolve and initiate antihypertensive therapy.

If ramucirumab is held for hypertension (ie, symptomatic hypertension, markedly elevated BP unresponsive to antihypertensive therapy), the dose of ramucirumab should be reduced to 6 mg/kg every other week upon re-treatment. A second dose reduction to 5 mg/kg every other week should be undertaken if an additional (third) postponement of therapy is required.

Grade 3 (systolic BP \geq 160 mm Hg or diastolic BP \geq 100 mm Hg; medical intervention indicated: more than 1 drug or more intensive therapy than previously used indicated)

- For Grade 3 hypertension not associated with symptoms, continue ramucirumab with more intensive antihypertensive therapy. If systolic BP remains >160 mm Hg or diastolic BP >100 mm Hg more than 2 weeks after initiation of additional antihypertensive therapy (as noted above), study ramucirumab will be held while continuing appropriate antihypertensive therapy.
- If hypertension is associated with symptoms, hold ramucirumab until symptoms resolve and initiate antihypertensive therapy.

[Type here]

[Type here]

[Type here]

Pembrolizumab + Ramucirumab (Ver 2.5, Oct 2024)

If ramucirumab is held more than once for hypertension (ie, symptomatic hypertension, markedly elevated BP unresponsive to antihypertensive therapy), the dose of ramucirumab should be reduced to 6 mg/kg every other week upon re-treatment. A second dose reduction to 5 mg/kg every other week should be undertaken if an additional (third) postponement of therapy is required.

Grade 4 or refractory

- Patients with Grade 4 hypertension (life-threatening consequences; eg malignant hypertension, transient or permanent neurologic deficit, hypertensive crisis; or urgent intervention indicated) or patients whose hypertension is poorly controlled (>160 mm Hg systolic or >100 mm Hg diastolic BP for >4 weeks) despite appropriate oral medication (>2 oral agents at maximum tolerated dose) will be discontinued from therapy.

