8. TREATMENT

8.1 Treatments Administered

8.1.1 Ramucirumab

Different drug product lots must not be mixed in a single infusion.

Patients will receive 8 mg/kg of ramucirumab every 2 weeks, administered as an I.V. infusion over approximately 1 hour (maximum infusion rate 25 mg/min). The dose of ramucirumab will be dependent upon the patient's baseline body weight in kilograms. This dose will be recalculated if there is a $\geq 10\%$ change in body weight from baseline. Refer to the IB for more details.

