8.4 Special Treatment Considerations

8.4.1 Dose Adjustments and Delays

Ramucirumab

Dose modifications are permitted for ramucirumab in the setting of non-life-threatening, reversible Grade 3 and 4 AEs (that is, fatigue, anorexia, or fever) that resolve to Grade ≤ 1 within 1 treatment cycle (approximately 2 weeks). In this setting, ramucirumab may be readministered. If a second
[Type here] [Type here] [Type here]

Pembrolizumab + Ramucirumab (Ver 2.5, Oct 2024)

instance of such an event occurs, ramucirumab should be subsequently readministered at a dose of 6 mg/kg every other week. A second dose reduction to 5 mg/kg every other week is permitted for this level of event (Grade 3 and 4). If a Grade 4 AE occurs and is deemed at least possibly related to ramucirumab, then ramucirumab should be discontinued except in specific case of Grade 4 fever or Grade 4 laboratory abnormalities. If Grade 4 fever or laboratory abnormalities resolve to Grade ≤ 1 or pretreatment baseline within one treatment cycle (approximately 2 weeks), treatment with ramucirumab may be continued at the discretion of the treating physician. Criteria for dose reduction in the setting of hypertension or proteinuria and other AESIs are detailed in Section 11

Patients who enter the study with symptoms or laboratory values equivalent to NCI-CTCAE Version 4.03 Grade 1 to 2 AEs should not have dose reductions related to the persistence or mild worsening of those symptoms or laboratory values; dose reductions may be warranted if worsening of symptoms or laboratory values is clinically significant in the opinion of the patient's physician. Asymptomatic Grade 3 to 4 laboratory abnormalities should not result in dose interruptions, modifications, or discontinuation of protocol therapy unless determined to be clinically significant by the patient's physician (or unless otherwise specified in this protocol).

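### Section 11.1.1 cuts ramucirumab after any hold in Grade <3 hypertension but only after a repeat hold in Grade 3, so the milder grade gets the larger first cut

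*Combined protocol and SAP*

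**What the plan says.** Section 8.1.1 sets the starting dose: "Patients will receive 8 mg/kg of ramucirumab every 2 weeks". Section 8.4.1 gives general reduction rules but passes hypertension on: "Criteria for dose reduction in the setting of hypertension or proteinuria and other AESIs are detailed in Section 11".

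Section 11.1.1 then has one block for Grade <3 and one for Grade 3. Both hold the drug for symptoms, in almost the same words: "If the hypertension is associated with symptoms, hold ramucirumab until symptoms resolve and initiate antihypertensive therapy" (Grade <3) and "If hypertension is associated with symptoms, hold ramucirumab until symptoms resolve and initiate antihypertensive therapy" (Grade 3). The reduction paragraphs that follow differ in their trigger:

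- Grade <3, where re-treatment is at 6 mg/kg: "If ramucirumab is held for hypertension (ie, symptomatic hypertension, markedly elevated BP unresponsive to antihypertensive therapy), the dose of ramucirumab should be reduced". No number of holds is given.
- Grade 3: "If ramucirumab is held more than once for hypertension", with the same step to 6 mg/kg.

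Both paragraphs end with the same sentence: "A second dose reduction to 5 mg/kg every other week should be undertaken if an additional (third) postponement of therapy is required".

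**The concern.** A toxicity ladder would be expected to be at least as cautious for the more severe grade. Here it is less cautious at the first step: the same event, a first hold for symptoms, costs the Grade <3 patient a dose level and the Grade 3 patient none. No sentence states the dose after a first Grade 3 hold, so the investigator has to infer it.

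Section 11.1.6 describes hypertension as an identified risk of ramucirumab, so this is an operative safety rule. One of two errors follows. If a repeat hold was meant for both grades, a Grade <3 patient is reduced one hold too early and uses up one of the two reductions that Section 8.4.1 allows before ramucirumab must stop. If a cut at the first hold was meant, a Grade 3 patient restarts at full dose. In either case an investigator or monitor cannot be sure which dose complies.

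**Working it through.** The plan states no figure to reproduce. The check sets the two paragraphs side by side and applies them literally.

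Inputs: starting dose 8 mg/kg every 2 weeks (Section 8.1.1); first reduced dose 6 mg/kg and second reduced dose 5 mg/kg (Section 11.1.1, both blocks). Assumption: no earlier reduction for another reason.

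Dose in mg/kg on re-treatment after each hold, with all holds at one grade:

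| Hold | Grade <3 as written | Grade 3 as written | Both grades if a repeat hold is required |
|---|---|---|---|
| 1 | 6 | 8 (implied) | 8 |
| 2 | 6 (no rule for a second hold) | 6 | 6 |
| 3 | 5 | 5 | 5 |

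Size of the steps: (8 − 6)/8 = 25% and (8 − 5)/8 = 37.5%. After hold 1 the milder grade gets 6/8 = 75% of the dose given to the more severe grade. From hold 2 on, the two columns agree.

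Evidence on which trigger was intended:

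1. The 5 mg/kg step comes at an additional, third postponement. That follows naturally if the second hold produced the first cut. Under the Grade <3 wording the first hold produces it, and the second hold has no stated consequence.
2. The Grade <3 paragraph also lists markedly raised pressure that does not respond to treatment as a reason for a hold. The Grade <3 bullets hold for symptoms only. The listed reason matches the Grade 3 bullet on pressure still above 160/100 mm Hg after two weeks of added therapy. This looks like text carried over from Grade 3.
3. For other reversible Grade 3 and 4 events, Section 8.4.1 allows re-administration after the first, goes to 6 mg/kg at the second instance, and then permits 5 mg/kg. That is the Grade 3 hypertension pattern.
4. Against this, Section 11.1.4 (proteinuria) resumes at 6 mg/kg after the first interruption and goes to 5 mg/kg on recurrence. The protocol therefore uses both patterns.

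Other places that might reconcile the triggers do not. Section 8.4.1 defers to Section 11 and otherwise only limits the number of reductions. Appendix 2, under Cardiac Function, sets a stopping rule for Grade 4 hypertension only.

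**The case against.** The strongest reply is that this is an editorial slip with little reach. In Grade <3, hypertension controlled below 160/100 mm Hg and asymptomatic hypertension both continue treatment, so only symptomatic cases are held. Patients who enter with Grade 1 to 2 symptoms "should not have dose reductions related to the persistence or mild worsening of those symptoms or laboratory values", which narrows the group further. Symptomatic patients restart only once symptoms resolve, Grade 4 or refractory hypertension ends treatment, and the physician may stop for toxicity at any time. If the likelier explanation is right, the error is conservative: one early 25% reduction in a milder case. All of this stands and is why the severity is low. It does not remove the contradiction, because discretion does not tell a physician which dose the protocol requires.

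Two stronger readings are tempting. A reader might infer that the text leaves open whether holds at different grades are added together. The Grade 3 sentence counts holds for hypertension, and the final sentence counts postponements of therapy; neither is limited by grade. The natural reading is a count across grades.

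A reader might also infer that the protocol wrongly returns Grade 3 patients to full dose. That needs a cut at the first hold to have been the intent, and most of the evidence points the other way.

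**Conclusion.** Wrong as written, low severity. The two triggers in Section 11.1.1 contradict each other in direction: after a first symptomatic hold from 8 mg/kg, Grade <3 restarts at 6 mg/kg and Grade 3, by implication, at 8 mg/kg. The discrepancy is one dose level, at the first hold only.

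The likeliest cause is that *more than once* dropped out of the Grade <3 paragraph. This is an inference from the third-postponement wording and the Section 8.4.1 ladder. The proteinuria rule shows that a cut at first resumption is also used, so the sponsor has to confirm the intent. The documents give no rate of symptomatic holds, so the number of patients affected cannot be calculated; with a planned maximum of 26 patients in Section 12 and so narrow a trigger, it should be few. The Simon two-stage design and the response-rate analysis are unaffected.

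**What to change.** Add *more than once* to the Grade <3 reduction paragraph in Section 11.1.1, and add a sentence to both blocks saying that after a first hold ramucirumab resumes at the current dose. Both grades then follow 8 / 6 / 5 mg/kg after holds 1 / 2 / 3, which fits the third-postponement wording already there.

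If the sponsor instead intends a cut at the first hold, delete *more than once* from the Grade 3 paragraph and change *third* to *second* in both blocks. Both grades would then go to 6 mg/kg after hold 1 and 5 mg/kg after hold 2, and a later event needing a reduction would fall under the two-reduction limit in Section 8.4.1.

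Either version is a wording amendment to one section. It adds no procedures, visits or patients.
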